### **6.2.1. Logistic Regression Model**

Treatment comparisons of discrete/binary efficacy variables between treatment groups will be made using a logistic regression analysis adjusted for baseline stratification variables (Section 6.1.4). The p-value and odds ratio with 100(1- $\alpha$ )% confidence interval (CI) from the logistic model will be reported.

Point estimates for proportions and difference in proportions will be presented. Confidence intervals and p-values for the estimates of the differences of the proportions and will be presented. For last-observation-carried-forward (LOCF) analyses the CIs will be based on the Newcombe-Wilson method without continuity correction. For multiple imputation analyses, percentages will be based on the observed percentages; CIs will be based on the Wald method without continuity correction.

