### 6.4.3. Multiple Imputation

A multiple imputation method will be used to impute the missing NIAID-OS scores (Rubin, 1996). The multiply-imputed datasets will be used for the primary analyses of several endpoints involving the NIAID-OS scores. A total of 100 multiply-imputed datasets will be generated. For random number generation, the seed will be set 3012021. The multiple imputation will be performed in a stratified manner with the imputation performed separately for each of the following levels: (1) baricitinib patients with baseline NIAID-OS of 5 or 6 and baseline steroid use, (2) baricitinib patients with baseline NIAID-OS of 5 or 6 and no baseline steroid use, (3) other baricitinib patients, (4) comparator patients with baseline NIAID-OS of 5 or 6 and baseline steroid use, (5) comparator patients with baseline NIAID-OS of 5 or 6 and no baseline steroid use, and (6) other comparator patients. In all these strata, baseline steroid use is defined as in Section 6.1.4. These strata are slightly reduced from what might be expected in order to keep a sufficient number of patients in each stratum. Imputation will be performed using a Markov model where each transition to a future state is dependent on only the previous state. This approach is described in detail in [Appendix 2](#).

The intended estimand for the multiple imputation approach is based on the treatment policy strategy for handling intercurrent events (ICH E9R [ICH 2017]). In this strategy the value of the NIAID-OS score is the value of interest regardless of any intercurrent events that occurred. The NIAID-OS includes a state for death, and thus it is meaningful even for patients who have died.

If the between-imputation variance calculated while combining some analysis results of the multiply-imputed datasets is zero then that specific analysis will not be performed using multiple imputation. Instead, the observed data will be used to perform the same analysis.

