**Table KHAA.6.5. Description of Primary, Key Secondary, and Associated Supportive Analyses**

Measure	Variable	Population	Analysis Method	Time Point	Analysis Type
NIAID-OS	Proportion of patients who died or progressed to non-invasive ventilation or high-flow oxygen (OS $\geq$ 6)	ITT: Population 1 - all randomized patients	Logistic regression using MI	By Day 28	Primary analysis
		ITT: Population 2 – patients who, at baseline, require oxygen supplementation and are not receiving dexamethasone or other systemic corticosteroids for the primary study condition.	Logistic regression using MI	By Day 28	Primary analysis
		ITT	Logistic regression using LOCF	By Day 28	Supportive analysis
		ITT: Population 2	Logistic regression using LOCF	By Day 28	Supportive analysis
		Safety Population	Logistic regression using MI	By Day 28	Supportive Analysis
		ITT Population, excluding patients who die within 24 hours of baseline and have Do Not Resuscitate (DNR) or Do Not Intubate (DNI) orders	Logistic regression using MI	By Day 28	Sensitivity Analysis
		Ventilator free days (VFD)	ITT	ANOVA using MI	By Day 28
	Wilcoxon rank-sum test using LOCF			By Day 28	Supportive analysis
	Proportion of patients with 1-point improvement	ITT	Logistic regression using MI	Day 4, 7, 10, 14	Key secondary analysis
			Logistic regression using LOCF	Day 4, 7, 10, 14	Supportive analysis

Measure	Variable	Population	Analysis Method	Time Point	Analysis Type
	Time to recovery	ITT	Log-rank test using IETI	By Day 28	Key secondary analysis
			Cox proportional hazards model using IETI	By Day 28	Supportive analysis
			Max-combo test using IETI (if needed)	By Day 28	Supportive analysis
NIAID-OS	Overall improvement	ITT	Proportional odds model using MI	Day 4, 7, 10, 14	Key secondary analysis
			Proportional odds model using LOCF	Day 4, 7, 10, 14	Supportive analysis
	Duration of hospitalization	ITT	ANOVA using MI	By Day 28	Key secondary analysis
			Wilcoxon rank-sum test LOCF	By Day 28	Supportive analysis
	All-cause mortality	ITT	Log-rank test	By Day 28	Key secondary analysis
			Cox proportional hazards model	By Day 28	Supportive analysis
Safety					
			Log-rank test	By Day 28	Supportive analysis
			Cox proportional hazards model	By Day 28	Supportive analysis
Oxygen Saturation	Proportion of patients with change in oxygen saturation from <94% at baseline to $\geq$ 94% at the observed time point	ITT	Logistic regression using LOCF	Day 4, 7, 10, 14	Key secondary analysis

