For subgroup analyses of categorical endpoints, a logistic regression model or proportional odds model using the Firth correction (Firth 1993) will be used to obtain a p-value for the treatment-by-subgroup interaction. The response variable will be each corresponding endpoint. The explanatory variables will be treatment, subgroup, treatment-by-subgroup interaction, and the baseline stratification variables (Section 6.1.4). Within each subgroup category, odds ratios (bariatric 4-mg over placebo) and associated CIs and p-values will be provided. Point estimates and CIs of the proportions and difference in proportions will be presented. For LOCF analyses the CIs will be based on the Newcombe-Wilson method without continuity correction. For multiple imputation analyses, proportions/percentages will be based on percentages in the multiply-imputed datasets; CIs will be based on the Wald method without continuity correction.

For ANOVA analyses of continuous endpoints, the following explanatory variables will be included for the test of interaction: treatment, subgroup, treatment-by-subgroup interaction and the baseline stratification factors (Section 6.1.4). The F test will be used to obtain a p value for treatment-by-subgroup interaction, type III sums of squares. Within each subgroup category, LS mean and associated p-values from ANOVA (using models given in Section 6.2.2) will be provided.

For the time-to-event endpoints, an unstratified log-rank test will be performed within each level of specified subgroups if sample sizes allow. Analysis of individual levels of subgroups will follow what is specified in Section 6.2.3, possibly with the use of the Firth correction.

Descriptive statistics will be provided for each treatment and stratum of a subgroup, regardless of sample size. Inferential statistics will be provided if sample sizes and event numbers are sufficiently large (e.g., >100 patients total and at least 1 event in each arm).

Additional subgroup analyses on efficacy may be performed as deemed appropriate and necessary.

Subgroup analyses for safety parameters will be specified in the List of Analyses for this study.

[Table KHAA.6.12](#) lists the analysis methods for the different subgroup analysis.

Table KHAA.6.12. Description of Subgroup Analyses for Primary and Key Secondary Endpoints

Measure	Variable	Subgroup	Analysis Method	Time Point

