The overall likelihood may be found by multiplying together the likelihoods from each patient. As described by Rubin (1976) the maximum likelihood estimator after marginalizing out the missing observations is still asymptotically unbiased under a missing at random (MAR) assumption. Maximum likelihood estimates of the model parameters ( $\boldsymbol{\theta}$ ) may be calculated using the expectation maximization (EM) algorithm. The same algorithms commonly used for “hidden Markov models” (HMMs) may be equally applied to the Markov model with missing data. The EM algorithm in this context is known as the Baum-Welsh algorithm in the HMM literature. A standard algorithm can be used to simulate from the distribution of the missing data conditional on the observed data (i.e., simulate from  $\mathbf{P}_{\boldsymbol{\theta}}(\mathbf{H}_i^{mis} | \mathbf{H}_{i,1:T}^{obs})$ ).

As described by Honaker and King (2010), a bootstrap + EM procedure is used to appropriately account for model uncertainty. The imputation proceeds by performing the following steps for  $m \in \{1, 2, \dots, M\}$  with  $M = 100$ :

1. Generate a bootstrapped dataset by resampling patients with replacement.
2. Estimate the model parameters using the maximum likelihood approach as calculated using the EM algorithm. For iteration  $m$  the bootstrapped parameter estimates are  $\tilde{\boldsymbol{\theta}}_m$ .
3. Impute the missing data in the original data (i.e., not the bootstrap data) by simulating from the distribution of the missing states conditional on the observed states assuming the estimated bootstrap model parameters (i.e., simulate from  $\mathbf{P}_{\tilde{\boldsymbol{\theta}}_m}(\mathbf{H}_i^{mis} | \mathbf{H}_{i,1:T}^{obs})$ ).

The above steps are applied 100 times to generate 100 multiply imputed datasets. We note that with MMMI covariates can be accounted for by using a stratified imputation approach where imputation is performed separately for each strata. The mathematical details of the MMMI algorithm is provided in the following section.

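### For multiple-imputation analyses SAP 6.2.1 takes percentages from observed data, so the primary endpoint's reported risk difference handles missing data differently from its odds ratio and p-value

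*SAP*

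**What the plan says.** SAP Table KHAA.6.5 gives the primary analysis in both Population 1 and Population 2 as "Logistic regression using MI". SAP 6.4.3 says: "The multiply-imputed datasets will be used for the primary analyses of several endpoints involving the NIAID-OS scores". It sets the number of datasets at 100. Appendix 2 supports the imputation model by noting that its estimator "is still asymptotically unbiased under a missing at random (MAR) assumption".

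SAP 6.2.1 specifies two kinds of result for a binary endpoint. One is the p-value and the odds ratio, whose "confidence interval (CI) from the logistic model will be reported". The other is on the absolute scale: "Point estimates for proportions and difference in proportions will be presented", followed by confidence intervals and p-values for the difference. For the absolute scale it adds: "For multiple imputation analyses, percentages will be based on the observed percentages", with Wald intervals and no continuity correction.

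SAP 6.14 has a nearly parallel sentence for subgroups with the opposite rule: "For multiple imputation analyses, proportions/percentages will be based on percentages in the multiply-imputed datasets". Table KHAA.6.12 applies multiple imputation (MI) to the primary endpoint by baseline disease severity, so that rule governs the same endpoint.

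Two other places matter. Table KHAA.6.1 has a general rule for categorical summaries: counts may be observed or imputed, and the denominator is the whole analysis population. Table KHAA.6.4 treats the primary endpoint as missing only when the ordinal score is missing and the patient's status cannot be worked out from other data.

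**The concern.** A patient whose Day 28 status is undetermined is imputed for the odds ratio but has no observed outcome for the percentage. The absolute and relative effects for one primary endpoint would then appear side by side on different missing-data assumptions. SAP 6.4.3 ties the imputation to a treatment-policy estimand; a difference of observed percentages does not target the same quantity unless missingness is negligible.

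The missingness is not neutral. The event is cumulative, so a patient lost after an event is a known event and only event-free patients can be missing. Leaving them out raises an arm's rate whenever their later risk is below that arm's overall rate.

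The absolute difference will be read closely. Protocol 9.4.1 commits to reporting it with a 95% interval, and Protocol 9.2 justifies the sample size in absolute differences.

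**Working it through.** **Figures from the documents.** Protocol 9.2 assumes a placebo event rate of about 25% (Amendment D). With 500 per arm and two-sided 0.05, a two-proportion power calculation gives 47.3% for a 5-point difference and 82.7% for 7.5 points, matching the stated 47% and 83%. The Amendment E table gives a combined effect of 0.054, which is 0.6 × 0.040 + 0.4 × 0.075. I therefore take true rates of 25% and 25 − 5.4 = 19.6%. Neither document states a figure for the percentage rule itself; that part rests on the wording.

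**Assumptions (not in the documents).** The event-free missing share m is 3-6% per arm. The later event risk q of those patients is 5-15%, the same in both arms.

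**Formulas.** With true rate p:

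- complete-case rate = (p − mq) / (1 − m)
- rate with missing counted as non-event = p − mq
- imputation that recovers q returns p, hence 5.4 points.

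**One case in full.** Placebo m = 6%, baricitinib m = 3%, q = 5%, complete cases: (0.25 − 0.003)/0.94 = 26.28% and (0.196 − 0.0015)/0.97 = 20.05%. The difference is 6.23 points.

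| Handling of missing | Placebo m | Baricitinib m | Difference, q = 5% | Difference, q = 15% |
|---|---|---|---|---|
| Complete cases | 3% | 3% | 5.57 | 5.57 |
| Complete cases | 6% | 6% | 5.74 | 5.74 |
| Complete cases | 6% | 3% | 6.23 | 5.90 |
| Complete cases | 3% | 6% | 5.09 | 5.42 |
| Non-event | 6% | 3% | 5.25 | 4.95 |
| Non-event | 3% | 6% | 5.55 | 5.85 |

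With equal dropout the complete-case difference is 5.4/(1 − m), an inflation of 3.1% to 6.4%. Counting missing as non-event leaves it at 5.4. With unequal dropout the sign depends on which arm loses more patients and on which denominator is used.

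**Scale.** With 700 per arm and 175 against 140 events, the Wald 95% half-width is 1.96 × √(0.25 × 0.75/700 + 0.20 × 0.80/700) = 4.4 points. The largest shift in the table is 0.83 points.

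**Effect on the p-value for the difference.** Take 700 per arm with 175 and 145 known events, and simple Wald tests with no between-imputation variance added.

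- 5% of placebo and 3% of baricitinib missing: complete cases give 175/665 against 145/679, a difference of 4.96 points, p = 0.033. Imputed percentages give p = 0.051, 0.047 or 0.035 when 5%, 10% or 25% of the missing are imputed as events.
- Shares reversed: complete-case p = 0.087; imputed p = 0.063, 0.070 or 0.096.

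So in a borderline trial the extra p-value can fall on the other side of 0.05 from one based on the imputed data, but only for some inputs.

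**The case against.** The strongest reply is that this is a reporting inconsistency with little consequence. Much of that reply stands.

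- **Confirmatory inference.** A reader might infer that the primary test is compromised. It is not: success is decided by the MI logistic test under the scheme in SAP 6.6. SAP 6.2.1 does not rank the risk difference above the odds ratio.
- **Direction.** A reader might infer that observed percentages always flatter baricitinib. The table shows they need not. SAP 6.2.1 does not define the denominator; if the whole-population rule in Table KHAA.6.1 governs, the patient set is the full ITT set and arm rates are understated. The missing-data assumption would still differ from the MI model's.
- **Interval.** A reader might infer that the Wald interval ignores imputation uncertainty. The text does not settle this. The observed-data clause governs percentages; the interval clause names only the method, and SAP 6.14 uses the same Wald wording beside imputed percentages.
- **Second p-value.** SAP 6.2.1 asks for a p-value for the difference in any case, and the correction below would still produce one.
- **Subgroups.** Only the baseline-severity subgroups use MI for the primary endpoint. The other subgroups use LOCF, so the failure to reconcile is confined to one family.
- **Mitigation.** The LOCF supportive analyses give a risk difference that keeps dropouts who have a postbaseline value. SAP 6.4 and Table KHAA.6.4 allow status to be derived from other data, and Protocol 8.1.1 has hospitalization status completed daily whatever the discharge status or contact, so missingness may be low.

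The mismatch would vanish only if observed percentages meant raw, unadjusted percentages within the imputed datasets. The SAP does not say so, and the contrast with SAP 6.14 points the other way.

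**Conclusion.** The point holds in a limited form. SAP 6.2.1 states a rule, rather than merely leaving out detail, that puts the reported risk difference on a different missing-data basis from the odds ratio and p-value, and SAP 6.14 states a conflicting rule for the same endpoint. Two programmers could follow the SAP and produce different tables.

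Under the assumed dropout the distortion runs from a few tenths of a point below a true 5.4-point difference to about 0.8 above it. That is small against the interval width, and smaller still if missingness is low and balanced. The dropout rates, the later event risk and its equality across arms are all assumptions. The documents do not support a claim of systematic overstatement or any claim against the confirmatory result. What is affected is the reported absolute effect and the interval and p-value attached to it.

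**What to change.** Change SAP 6.2.1 so that, for MI analyses, the arm proportions, their difference and the Wald variance are computed in each of the 100 imputed datasets and pooled by Rubin's rules. This agrees with SAP 6.14 on percentages and settles how the variance is obtained. Observed percentages can stay as a descriptive line, labelled as such and shown with their denominators.

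The cost is one sentence of SAP text and a small programming change. The imputed datasets are already required for the primary test, so no new data or imputation is needed.

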### **6.2.2. Analysis of Variance**

Treatment comparisons of quantitative efficacy and health outcome variables will be made using analysis of variance (ANOVA) adjusted for baseline stratification variables (Section 6.1.4). Where appropriate, baseline value for the endpoint of interest will also be included in the model. Type 3 tests for least squares (LS) means will be used for statistical comparison between treatment groups. The LS mean difference, standard error, p-value, and 95% CI will also be reported.

### **6.2.3. Time-to-Event Analysis**

The primary analysis for time-to-event analysis will be the unstratified log-rank test. Treatment comparisons for time-to-event analysis may also be analyzed using a Cox proportional hazards model adjusted for baseline stratification variables (Section 6.1.4). The hazard ratio with 95% CIs will be reported. Kaplan-Meier curves may also be produced. Diagnostic tests for checking the validity of the proportional hazards assumption may be performed. If the assumption of proportional hazards is not justified, a statistical model capable of handling nonproportional hazards will be explored to assess treatment effect, such as a max-combo test (Lee 1996), restricted mean survival time model (Royston and Parmar 2013), and win ratio analysis (Pocock et al. 2012).

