## 5.3. Method of Assignment to Treatment

Blinding will be maintained in the Phase 3 study.

Method of treatment assignment

Patients who meet all criteria for enrollment will be randomized in a 1:1 ratio (baricitinib 4-mg: placebo) at Day 1.

Randomization will be stratified by these factors:

- disease severity by ordinal scale (OS):
  - hospitalized not requiring supplemental oxygen, requiring ongoing medical care (OS 4)
  - hospitalized requiring supplemental oxygen by prongs or mask (OS 5)
  - hospitalized requiring non-invasive ventilation or high-flow oxygen (OS 6)
- age (<65 years; ≥65 years)
- region (US, Europe, rest of world), and
- dexamethasone and/or other systemic corticosteroid used at baseline for primary study condition (Yes/No). (Note that the original protocol included symptom onset <7 days or ≥7 days prior to randomization as a stratification factor. It was changed to this one in Amendment (c).)

Assignment to treatment groups will be determined by a computer-generated random sequence using an interactive web-response system (IWRS).

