### 6.1.2. Definition of Study Baseline

Unless otherwise specified, for efficacy and health outcomes, baseline is defined as the last nonmissing assessment recorded on or prior to, the first date that clinical status is assessed.

Baseline for safety analyses is described in [Table KHAA.6.8](#).

Change from baseline will be calculated as the visit value of interest minus the baseline value. If a baseline value or the value at the visit is missing for a variable, then the change from baseline is defined as missing.

The baseline of vital signs is defined as the vital signs collated at Day 1 from the case report form (CRF) Assessment for the National Early Warning Score (NEWS) (AVPU1001\_VS1001\_F1). The post baseline vital signs for analyses other than NEWS is defined as vital signs collated from CRF Vital Signs: Minimum and Maximum (VS1001).

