### 6.1.4. Baseline Stratification Variables

Throughout the SAP, when baseline stratification variables are referred to, they include the following categorical variables:

- baseline disease severity (ordinal scale [OS] 4, OS 5, OS 6),
- age (<65 years, ≥65 years),
- region (US, Europe, rest of world) and
- dexamethasone and/or other systemic corticosteroid used at baseline for primary study condition (Yes/No).

If any of these are redundant for a particular model they will be dropped.

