### **6.2.4. Proportional Odds Model**

The proportional odds model will be used to assess the overall improvement in the OS. Treatment comparisons will be adjusted for baseline stratification variables (Section 6.1.4). The treatment odds ratio estimated from the model will be presented along with the CI and p-value.

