### **6.2.5. Wilcoxon Rank-Sum Test**

The Wilcoxon rank-sum test, without continuity correction, will be used for analyzing endpoints associated with number of days, such as number of ventilator free days. The p-value for each treatment group will be provided.

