## 6.6. Multiple Comparisons/Multiplicity

Multiplicity controlled analyses will be performed on the primary and key secondary endpoints to control the overall family-wise Type I error rate at a 1-sided  $\alpha$  level of 0.025. The graphical multiple testing procedure described in Bretz et al. (2011) will be used. The graphical approach is a closed testing procedure; hence it strongly controls the family-wise error rate (FWER) across all endpoints (Alosh et al. 2014).

[figure not shown]
See [Figure KHAA.6.1](#) for the graphical testing scheme for this study. This scheme allows for some  $\alpha$  to be sent to the key secondary analyses if Population 1 achieves statistical significance (see next paragraph). Note that for the 2 primary populations the scheme is slightly different from what is in the protocol. As the testing scheme only impacts interpretation of the results and not the actual analysis, there is no plan to update the protocol.

If Population 2 is rejected at  $\alpha_2$ , Population 1 will be tested at level  $\alpha$ , otherwise Population 1 will be tested at level  $\alpha_1$ . If Population 1 is rejected, each of the gated secondaries will be tested in order until one is not rejected as depicted in [Figure KHAA.6.1](#). The key secondaries will be tested at level  $\alpha_1$  if Population 1 was rejected or at level  $\alpha$  if both Population 1 and Population 2 were rejected. Finally, if Population 1 and all secondaries are rejected at level  $\alpha_1$ , but Population 2 was not rejected at level  $\alpha_2$ , Population 2 will be tested again at level  $\alpha$ .

The testing scheme will provide a strong control of Type-I error for the study at a 1-sided 0.025 level and is based on the closed testing principle (Marcus et al. 1976). The testing scheme is parametric, where the known correlation is accounted for between the 2 test statistics  $z_1$  and  $z_2$ . The initial significance levels for the Primary endpoints Population 1 ( $\alpha_1$ ) and Population 2 ( $\alpha_2$ ) will be computed using the fact that their test statistics have a correlation of  $\sqrt{p}$  where  $p$  is the percentage of Population 2 within Population 1 observed in the final analysis data set and a 0.99 weight on Population 1 and 0.01 weight on Population 2. The two significance levels will be computed using the R package gMCP.

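### Possible efficiency gain: the gated log-rank tests for time to recovery and mortality do not use baseline OS, although randomization is stratified by it; valid, but conservative if OS is at least moderately prognostic

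*SAP*

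**What the plan says.** - **Test.** SAP 6.2.3: "The primary analysis for time-to-event analysis will be the unstratified log-rank test". A Cox model adjusted for the stratification variables may be added. Table KHAA.6.5 lists "Log-rank test using IETI" as the key secondary analysis of time to recovery and a log-rank test as the key secondary analysis of all-cause mortality. The Cox models are supportive.
- **Randomization.** SAP 5.3: "Randomization will be stratified by these factors", and the list is disease severity by OS, age, region and baseline corticosteroid use. SAP 6.1.4 carries the same factors into the analysis, including "baseline disease severity (ordinal scale [OS] 4, OS 5, OS 6".
- **Other gated analyses.** SAP 6.2.1 (logistic) and 6.2.2 (ANOVA) adjust for these factors, as does 6.2.4 (proportional odds): "Treatment comparisons will be adjusted for baseline stratification variables (Section 6.1.4".
- **Wilcoxon.** SAP 6.2.5: "The Wilcoxon rank-sum test, without continuity correction, will be used for analyzing endpoints associated with number of days". It is also unadjusted, but Table KHAA.6.5 labels it supportive. For ventilator-free days I therefore read the ANOVA row as the key secondary analysis.
- **Gating.** SAP 6.6: "If Population 1 is rejected, each of the gated secondaries will be tested in order until one is not rejected". The order is in Figure KHAA.6.1, which is not reproduced in the text available to me.
- **Protocol.** Section 9.4.1 names a log-rank test without saying stratified or unstratified.

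**The concern.** Allocation is balanced within OS strata, but the unstratified log-rank computes its variance as if it were not. If OS predicts recovery, that variance is too large and the test rejects less often than its nominal level allows. Mixing patients with different recovery rates also dilutes the marginal effect. Both reduce power.

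Time to recovery sits in a fixed sequence that stops at the first non-rejection, so power lost there also lowers the chance of testing anything placed behind it. The adjusted Cox model cannot rescue a missed gate, because it is only supportive.

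**Working it through.** **1. Is there a plan figure to reproduce?** No. The documents state no power, event count or effect size for time to recovery.

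**2. Inputs.** From the documents: about 1400 patients (SAP 5.2); 1:1 allocation stratified by OS, age, region and steroid use (SAP 5.3); 60% steroid use (the planning figure in SAP 5.2); deaths treated as never recovering, censored at Day 28 (SAP 6.4.1); one-sided 0.025 (SAP 6.6). With the 0.99 weight, α1 is about 0.0248 to 0.0249 if Population 2 is 10 to 40% of Population 1 (assumed), so 0.025 is close enough.

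Assumed, because the documents are silent: OS 4/5/6 mix 15/60/25% (alternative 5/65/30%); blocks of 4; exponential recovery times in whole days; modest age effects; and 28-day control recovery for OS 4/5/6 of
- weak: 88/82/68%
- moderate: 90/83/60%
- strong: 93/84/50%

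The implied OS 5 to OS 6 rate ratio is ln(1−p5)/ln(1−p6). Weak: ln 0.18/ln 0.32 = 1.5. Moderate: ln 0.17/ln 0.40 = 1.9. Strong: ln 0.16/ln 0.50 = 2.6.

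**3. Why the test is conservative.** Under stratified randomization, true variance divided by the variance the test uses is R = 1 − Var(E[M|OS])/Var(M), where M is the null martingale residual. The actual one-sided level is 1 − Φ(1.96/√R). For a nearby set of assumed rates (mix 15/60/25):

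| Recovery OS 4/5/6 | R | 1.96/√R | Actual level |
|---|---|---|---|
| 85/80/72% | 0.987 | 1.973 | 0.0243 |
| 90/82/60% | 0.927 | 2.036 | 0.0209 |
| 95/85/45% | 0.796 | 2.197 | 0.0140 |

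Simulation of the last row gives 0.017 under stratified randomization and 0.026 under simple randomization (10,000 trials each, Monte Carlo SE about 0.0016). The unused stratification is therefore the cause. For the three scenarios in step 2 (40,000 trials each), the unstratified level is 0.0232, 0.0201 and 0.0162, and the OS-stratified level is 0.0250, 0.0240 and 0.0245.

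**4. Power for time to recovery, common rate ratio 1.15** (8,000 trials, mix 15/60/25, SE of the paired difference 0.1 to 0.35 points):

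| OS prognosis | Unstratified | Stratified | Gain |
|---|---|---|---|
| None | 65.7% | 65.6% | −0.1 |
| Weak | 63.1% | 65.3% | +2.2 |
| Moderate | 59.1% | 63.5% | +4.4 |
| Strong | 53.5% | 62.3% | +8.8 |

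Mix 5/65/30 gives +1.9, +4.5 and +8.8. With a weaker gradient (85/80/72%, OS 5 to OS 6 ratio 1.26) there is no visible gain: 64% and 64%.

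**5. Dependence on the effect size** (approximate gain, weak/moderate/strong):

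| Common ratio | Gain (points) |
|---|---|
| 1.10 | +2/+5/+8 |
| 1.15 | +2/+4/+9 |
| 1.20 | +1/+3/+6 |
| 1.25 | +1/+2/+4 |
| 1.30 | 0 to +1 |

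The gain shrinks because power is already high. A simpler run without age effects (3,000 trials per point) gave 95.9 vs 96.4, 95.5 vs 96.6 and 93.8 vs 96.5 at 1.25, slightly smaller than the table.

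**6. If the relative effect varies with OS** (unstratified vs stratified, weak/moderate/strong, mix 15/60/25):
- OS 4 null, 1.17 in OS 5 and 6: 60.7 vs 60.3, 56.6 vs 58.0, 51.8 vs 56.2. Over both mixes, about 0 to +7.
- Smaller effect with steroids (1.21 without, 1.11 with, OS 4 null): 49.8 vs 50.0, 46.2 vs 48.4, 41.3 vs 46.4, or about 0 to +5.
- Mild gradient 1.05/1.12/1.25: 59.6 vs 57.3, 55.4 vs 54.0, 50.0 vs 50.8, or about −2 to +1 (+2 at most with mix 5/65/30).
- Benefit concentrated in OS 6 (1.0/1.1/1.35): 61.6 vs 56.3, 57.8 vs 52.3, 52.4 vs 47.1. Over both mixes, about −4 to −6.

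**7. Mortality, hazard ratio 0.70 (assumed).** Weak (28-day death 7/10/15%): 52.5 vs 52.6. Strong (3/9/25%): 53.1 vs 55.2. The gain is 0 to +2.

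**The case against.** The strongest reply is that this was a deliberate, prespecified choice. SAP 6.3 asks for adjustment unless otherwise specified, and 6.2.3 specifies otherwise. The revision history records that the time-to-event models were clarified in Version 4, and an adjusted Cox model is already there as support. This stands. A reader might infer a contradiction with the protocol or with 6.3, or a type I error problem. The documents support neither: Protocol 9.4.1 fits both versions of the test, and the unstratified test errs on the safe side.

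The sign and size of the gain are also not established. A reader might take the 9 points as the expected loss, but that needs strong prognosis and a common ratio near 1.15, where the gain is close to its largest. Protocol 4.2 says the effect in the earlier trial was largest in patients requiring oxygen, and SAP 5.2 allows that steroids may reduce it. Scenarios built on those two statements give about 0 to +7. The loss scenario needs a relative benefit that rises from OS 5 to OS 6, which the documents do not state but cannot exclude.

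The gain is conditional as well. SAP 5.2 puts the chance that at least one primary succeeds at 54% or 81% in its two scenarios (illustrative 75% alpha split), and Population 1 cannot be rejected more often than that. If the tests were independent, 4 points would become at most about 4 × 0.81 = 3.2 or 4 × 0.54 = 2.2. They are correlated, so this is only a guide.

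Finally, a change at this stage follows an unblinded interim in January 2021 and needs a written justification.

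**Conclusion.** The point holds as an optional improvement. The two log-rank tests are the only gated analyses that ignore a factor used in randomization. They are valid, and conservative when OS is at least moderately prognostic for the outcome.

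Under the assumptions above, stratifying the time-to-recovery test gains about 2 to 9 points at a common ratio of 1.10 or 1.15, 1 to 6 at 1.20, 1 to 4 at 1.25, and at most 1 at 1.30. It gains nothing if OS is not prognostic or only very weakly so, and loses 4 to 6 points if relative benefit is concentrated in OS 6. Mortality adds 0 to 2. All of this is realised only when Population 1 is rejected and the sequence reaches the endpoint. How many endpoints lie behind time to recovery cannot be checked here.

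Confidence is high on the facts and on the direction of the conservatism, and medium on the benefit, because recovery rates, OS mix and effect size are all assumed.

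**What to change.** Before the study team is unblinded, and without use of unblinded interim results:

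1. In SAP 6.2.3 and Table KHAA.6.5, make the log-rank tests for time to recovery and all-cause mortality stratified by baseline OS as in 6.1.4. Keep the unstratified log-rank as supportive.
2. State whether the stratum comes from the IWRS or from recorded clinical status. SAP 6.1.2 points to the latter ("baseline is defined as the last nonmissing assessment recorded on or prior to, the first date that clinical status is assessed"), but 6.1.4 names no source. With 5% of patients in an adjacent IWRS category and analysis by true baseline OS, the gain at ratio 1.15 is essentially unchanged (62.4 vs 64.5, 58.3 vs 62.6, 53.0 vs 62.2).
3. Prespecify on blinded data when a sparse OS 4 stratum is merged into OS 5, since Protocol 5.1 now requires supplemental oxygen. Two strata cost almost nothing at ratio 1.15 (65.1/63.2/61.9 against 65.3/63.5/62.3 with three).
4. Say how a randomized patient with no recorded baseline OS is assigned, for example to the IWRS stratum, so that nobody is dropped. SAP Appendix 3 anticipates such patients.
5. Record that the change was made blind to treatment results, and name the downside: a loss of a few points if the relative effect rises with severity.

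The testing graph, the alpha levels, the other secondary log-rank tests and the subgroup tests stay as they are. The cost is one sentence, two table entries, a strata statement in the program, and the two rules in items 3 and 4. If the study team is already unblinded, do not change the gated test.
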